**Table 2 Definition of Adverse Events Causality**

| CAUSALITY        | ASSESSMENT
(all points should be reasonably complied with)   | CRITERIA |
|------------------|---|----------|
| Not related      | 
 
An AE with sufficient evidence to accept that there is improbable relationship to IMP administration (e.g., no temporal relationship to drug administration) and the disease, other drugs or other events provide plausible explanation)
 
                                |          |
| Possibly related | 
 
An AE with a reasonable time sequence to administration of the IMP, but which could also be explained by concurrent disease or other drugs or events. Information on drug withdrawal may be lacking or unclear.
 
   |          |
| Related          | 
 
An AE occurring in a plausible time relationship to IMP administration, and which cannot be explained by a concurrent disease or other drugs or events. The response to withdrawal of the drug (de-challenge) and rechallenge (if necessary), are clinically reasonable
 
 |          |

Outcome to Date are classified as follows:

- Fatal
- Not-Recovered/Not Resolved (ongoing) - AE is not recovered/resolved
- Recovered/Resolved – The patient has fully recovered from the AE with no residual effects observable
- Recovered/Resolved with sequelae – The patient has recovered from the AE with residual effects observable
- Unknown

AEs will be coded by data management using the Medical Dictionary for Regulatory Activities (MedDRA) AE dictionary, Version 18 or later.

### **Follow-up Reports for Non-Serious AEs**

All AEs, that do not meet any of the criteria for serious, should be regarded as non-SAEs and will be recorded on the AE eCRF. Severity and relationship to study medication will be assigned by the Investigator. Follow-up of AEs that occur during the study will continue until their satisfactory resolution or stabilization. In outstanding cases, it may be defined as “ongoing without further follow-up” by the Investigator and Sponsor’s decision.

#### **7.1.1 Adverse Events of Special Interest**

New or worsening acromegaly signs and/or symptoms will be recorded as adverse events of special interest (AESI) and are headache, fatigue, perspiration, soft tissue swelling, arthralgia, dysglycemia or hypertension or other signs that in view of the Investigator are related to acromegaly.

Worsening of symptoms will be any new sign/symptom or shift in severity (e.g. mild to moderate or moderate to severe). Severity will be defined according to [Table 1](#).

Worsening of dysglycemia is a shift in the severity criteria as defined in common terminology criteria for adverse events (CTCAE) v4.03 and shown in [Table 3](#).

Worsening of hypertension is defined as a shift in severity as defined in CTCAE v4.03 and shown in [Table 4](#).

**Table 3 Dysglycemia Severity criteria**

| Dysglycemia  | 1 (mild)  | 2 (moderate)  | 3 (severe)   | 4 (life threatening)   | 5 Death |
|--|---|---|--|--|---------|
| Hyperglycaemia
Definition: A disorder characterized by laboratory test results that indicate an elevation in the concentration of blood sugar. It is usually an indication of diabetes mellitus or glucose intolerance | Fasting glucose value:
>ULN -160 mg/dL;
>ULN - 8.9 mmol/L | Fasting glucose value:
>160 - 250 mg/dL;
>8.9 - 13.9 mmol/L | > 250 - 500 mg/dL
> 13.9 - 27.8 mmol/L
Hospitalization indicated | > 500 mg/dL
> 27.8 mmol/L
life-threatening consequences            | Death   |
| Hypoglycaemia
Definition: A disorder characterized by laboratory test results that indicate a low concentration of glucose in the blood  | <LLN - 55 mg/dL
<LLN - 3.0 mmol/L                            | < 55 - 40 mg/dL
< 3.0 - 2.2 mmol/L                             | < 40 - 30 mg/dL
< 2.2 - 1.7 mmol/L                                  | < 30 mg/dL
< 1.7 mmol/L
Life-threatening consequences;
seizures | Death   |

**Table 4 Hypertension Severity criteria**

| Severity             | Hypertension  |
|----------------------|---|
|                      | Definition: A disorder characterized by a pathological increase in blood pressure; a repeatedly elevation in the blood pressure exceeding 140 over 90 mm Hg.  |
| 1 (mild)             | Prehypertension (systolic BP 120 - 139 mm Hg or diastolic BP 80 - 89 mm Hg)   |
| 2 (moderate)         | Stage 1 hypertension (systolic BP 140 - 159 mm Hg or diastolic BP 90 - 99 mm Hg); medical intervention indicated; recurrent or persistent ( $\geq 24$ hrs); symptomatic increase by $>20$ mm Hg (diastolic) or to $>140/90$ mm Hg if previously WNL; monotherapy indicated
Pediatric: recurrent or persistent ( $\geq 24$ hrs) BP $>ULN$ ; monotherapy indicated |
| 3 (severe)           | Stage 2 hypertension (systolic BP $\geq 160$ mm Hg or diastolic BP $\geq 100$ mm Hg); medical intervention indicated; more than one drug or more intensive therapy than previously used indicated.  |
| 4 (life threatening) | Life-threatening consequences (e.g. malignant hypertension, transient or permanent neurologic deficit, hypertensive crisis); urgent intervention indicated  |
| 5 (death)            | Death   |

## 7.2 SERIOUS ADVERSE EVENTS

An SAE is any AE occurring at any dose that suggest a significant hazard or side effect, regardless of the Investigator or Sponsor's opinion on the relationship to the study medication and that result in, but may not be limited to, any of the following outcomes:

- Death (regardless of the cause)
- A life-threatening AE or suspected adverse reaction
- Inpatient hospitalization or prolongation of existing hospitalization (any inpatient hospital admission that includes a minimum of an overnight stay in a health care facility)
- A persistent or significant disability/incapacity or a substantial disruption of the ability to conduct normal life functions
- A congenital anomaly or birth defect
- Important medical events that may not result in death, be life-threatening, or require hospitalization may be **serious** when, based upon appropriate medical judgment, they may jeopardize the patient and may require medical or surgical intervention to prevent one of the outcomes listed above.

**Inpatient hospitalization or prolongation of existing hospitalization** means that hospital inpatient admission and/or prolongation of hospital stay were required for treatment of AE, or that they occurred as a consequence of the event.

Hospitalization for elective treatment of a pre-study condition that did not worsen while on study and optional hospitalizations not associated with a clinical AE (e.g., elective cosmetic surgery) are not considered SAEs.

**Important medical events** are those which may not be immediately life-threatening, but may jeopardize the patient and may require intervention to prevent one of the other serious outcomes listed above. Examples of such events are intensive treatment in an emergency room or at home for allergic bronchospasm; blood dyscrasias or convulsions that do not result in hospitalization; resulting in an AE will normally be considered serious by this criterion.

A **life-threatening** adverse drug experience is any AE that places the patient, in the view of the Investigator, at immediate risk of death from the reaction as it occurred, i.e., it does not include a reaction that, had it occurred in a more severe form, might have caused death.

## 7.3 DEFINITION OF AN UNEXPECTED ADVERSE EVENT

An **unexpected** adverse event is any AE, the specificity or severity of which is not consistent with information in the clinical protocol or current Investigator's Brochure for an unapproved study medication or package insert/summary of product characteristics for an approved product (package inserts are available separately at the participating center). Evaluation will be assessed separately for each of the IMPs in the study.

**Serious Unexpected Suspected Adverse Reaction (SUSAR)** is a serious adverse reaction assessed as unexpected by the Sponsor and that is judged by either the reporting Investigator or the Sponsor to have a reasonable causal relationship to a medical product.

#### 7.4 NOTIFICATION OF SERIOUS UNEXPECTED SUSPECTED ADVERSE EVENT

The Investigator is responsible for identifying, documenting, evaluating and reporting SAEs in accordance with the protocol, 21CFR312.32, 21CFR312.64, International Council for Harmonisation (ICH) guidelines, and all other applicable regulations.

##### Initial Notification

Upon identification, all SAEs will be reported by the site within 24 hours using the Initial SAE Report Form. The Initial SAE Report Form should be submitted to the contract research organization (CRO), Pharm-Olam within 24 hours either by e-mail (preferable) or by fax using the contact information provided below.

For regulatory purposes, the initial SAE reports should include:

- a) a suspected investigational medicinal product
- b) an identifiable patient (e.g., study patient code number)
- c) an AE with seriousness reason and the Investigator’s assessment of the relationship to study medication
- d) an identifiable reporting source (Investigator contact details)

SAEs should also be reported to the IRB/IEC according to local regulations.

Once reported, the SAE form and accompanying documentation should be placed in the Investigator’s site file.

In addition, all AEs / SAEs / SUSARs will be reported by the Sponsor to the IDMC, IRB/IEC and regulatory authorities as required by local regulations and ICH-GCP guidelines.

##### Follow-up of SAEs / SUSARs

Follow-up of SAEs / SUSARs that occur during the study will continue until their satisfactory resolution or stabilization. In outstanding cases, it may be defined as “ongoing without further follow-up” by the Investigator and Sponsor’s decision.

When supplementary information is available, a follow-up SAE Report Form must be completed by the site (marked as “follow-up report”). The contact report information for follow-up SAE reporting is the same as for initial SAE reports (see above section).

If supplementary information on a SAE has to be sent, the SAE form has to be used marked as “follow-up report” and should be placed in the SAE section of the Investigator’s site file.

Accompanying documentation, such as copies of hospital case reports, autopsy report, and other

documents when applicable, should be sent as soon as they are available.

Patients who have had an SAE during the treatment period must be followed clinically until all parameters (including laboratory) have either returned to normal or have stabilized or are otherwise explained.

Any newly emergent SAEs after treatment is discontinued or the patient has completed the study that is considered to be related to the study medication or study participation should be recorded and reported immediately to Pharm-Olam using the contact information as described above.

The Investigator will add the information on the SAE on the AE eCRF page and any other relevant eCRF. Particular attention will be made to ensure no discrepancies between the AE eCRF and the SAE form (i.e., outcome, severity, relationship must be consistent).

## **7.5 ANTICIPATED ADVERSE EVENTS**

Previous human experience and known AEs of octreotide are detailed in the corresponding IB.

## **7.6 OCTREOTIDE SAFETY GUIDANCE**

Below is the Sponsor's safety guidance for using octreotide in case of common GI adverse events, elevated liver function tests (LFTs) and/or blood sugar disorder. These guidelines should be used to guide treatment, however, in any case, should not replace clinical judgment.

### **Common Gastrointestinal Adverse Events**

In the previous Phase 3 Study (CH-ACM-01), GI symptoms were among the most commonly reported AEs. These AEs were generally transient and declined with time (median duration was 13 days). Most were mild to moderate in intensity, and occurred during the first two months. There was no dose relationship and most resolved with treatment continuation.

In patients who develop abdominal symptoms (e.g., nausea, vomiting, abdominal pain or diarrhea), common GI illnesses should be excluded (e.g., gastroenteritis, cholestasis, etc.), and treated accordingly. If symptoms are mild to moderate in intensity and patient is able to tolerate oral medications, consideration should be given to treating the patient symptomatically with anti-emetics or anti-diarrheals to determine if patient's GI symptoms will resolve on therapy. Patients who have severe or persistent symptoms or who cannot tolerate food/fluids should be discontinued.

Of note, a phase 1 study showed no interaction between loperamide and oral octreotide capsules.

### **Liver Dysfunction**

Somatostatin analogs including octreotide have been associated with liver function abnormalities, as well as sporadic post-marketing reports of acute hepatitis with or without cholestasis, jaundice and cholestatic jaundice.

Octreotide inhibits secretion of cholecystokinin, resulting in reduced contractility of the gallbladder and an increased risk of sludge and stone formation. Biliary disease is the most common reasons for liver dysfunction in acromegaly patients.

Liver function tests (ALT, AST and Bilirubin), will be monitored routinely at all scheduled visits during all periods of the study. Liver function tests could also be assessed at any unscheduled study visit, as clinically indicated.

Patients who develop liver function abnormalities (elevated transaminases to  $>3 \times \text{ULN}$ ) during the study should be evaluated for common causes of hepatitis such as cholestasis, alcoholic liver disease, non-alcoholic steatohepatitis, environmental exposures, other drug/herbal supplement exposures, viral or autoimmune hepatitis. The diagnostic work up of liver dysfunction should be guided by the patient's medical history and physical exam, and local practice, at the investigator discretion.

Patients with asymptomatic liver dysfunction (i.e., ALT or AST  $>3 \times \text{ULN}$  and  $< 5 \times \text{ULN}$  and total bilirubin  $< 2 \times \text{ULN}$ ), may continue to receive study drug (Figure 2). Liver function tests must be repeated in 7 days. In case of continued transaminase elevation, periodical follow up visits should be considered, per the investigator discretion up to resolution/return to baseline. Follow up should include monitoring of symptoms potentially associated with acute hepatitis (new appearance of fatigue, nausea, vomiting, right upper quadrant pain or tenderness, fever, rash, and/or eosinophilia), or with complications of cholestasis (e.g. cholangitis). In case of symptoms suggestive of cholestasis, a follow up abdominal ultrasound should be considered. Local assessment of INR could be added to the liver function tests, based on the investigator discretion.

[figure not shown]
All patients who develop significant liver dysfunction (ALT or AST  $\geq 5 \times \text{ULN}$ ) should have study drug held and be followed up within 3 days and every 3-4 days thereafter up to resolution/return to baseline. In case ALT/AST remains above  $5 \times \text{ULN}$ , study drug should be discontinued. If ALT/AST has fallen to  $>3 \times \text{ULN}$  and  $< 5 \times \text{ULN}$ , patients should be managed as described in the previous paragraph.

If liver function tests normalize or return to baseline, while study drug has been held, the decision to resume study drug must be discussed with the study medical monitor.

If no alternative etiology exists study drug should be discontinued in the following scenarios:

- ALT or AST  $>5 \times \text{ULN}$  for at least 2 weeks
- ALT or AST  $>3 \times \text{ULN}$  and (TBL  $>2 \times \text{ULN}$  or INR  $>1.5 \times \text{ULN}$ )
- ALT or AST  $>3 \times \text{ULN}$  with new appearance of fatigue, nausea, vomiting, right upper quadrant pain or tenderness, fever, rash, and/or eosinophilia ( $>5\%$ ).

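### The liver guidance does not agree with itself on when a hold for ALT or AST at or above 5 × ULN becomes permanent discontinuation

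*Protocol*

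**What the plan says.** All of the following stands in Protocol 7.6, under Liver Dysfunction, unless noted.

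- **Hold.** The rule covers anyone whose ALT or AST reaches 5 × ULN or more: such patients "should have study drug held and be followed up within 3 days and every 3-4 days thereafter up to resolution/return to baseline".
- **Discontinuation, general sentence.** "In case ALT/AST remains above" 5 × ULN, drug is to be discontinued. No length of time is given, and cause is not mentioned.
- **Discontinuation, list.** "If no alternative etiology exists study drug should be discontinued in the following scenarios": the first scenario is ALT or AST > 5 × ULN "for at least 2 weeks". The other two start at > 3 × ULN and add either a bilirubin or INR limit or new symptoms.
- **Partial fall on hold** (to > 3 and < 5 × ULN). Here "patients should be managed as described in the previous paragraph". That paragraph covers asymptomatic patients with bilirubin < 2 × ULN, who "may continue to receive study drug (Figure 2"), with a retest in 7 days. It does not mention the medical monitor.
- **Normal or baseline values on hold.** In this case "the decision to resume study drug must be discussed with the study medical monitor".
- **Status of the guidance** (opening of 7.6). "These guidelines should be used to guide treatment, however, in any case, should not replace clinical judgment".

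The link to the analysis is in Protocol 2.2.1 and SAP 5.1.1 and 6.8.1: a patient who stops study medication in the DPC period, whatever the reason, is a primary non-responder whatever the IGF-1. Under Protocol 4.6.1, stopping for a reason other than the pre-defined withdrawal criteria also excludes the patient from the OLE.

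**The concern.** Two statements a few lines apart answer the same question: when does a hold become permanent? They differ on two elements, time above the threshold and the role of another cause. An investigator following the general sentence and one following the list could reach different decisions on identical laboratory courses.

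Cause is not a side issue in this section. It asks for an etiology work-up above 3 × ULN and names biliary disease as the most common reason for liver dysfunction in these patients. A patient with another cause found is therefore a case the guidance should expect.

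Two things are at stake. The first is consistent handling of a hepatic safety event across sites. The second is the trial outcome: in a study of about 50 patients, whether a liver event ends as a temporary hold or as permanent discontinuation can decide a patient's responder status and access to the extension.

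**Working it through.** The plan gives no figure to reproduce here. The check sets the two discontinuation statements side by side and applies each to the same course. In every row drug is already on hold.

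| Course while on hold | General sentence | List, > 5 × ULN scenario |
|---|---|---|
| Still > 5 × ULN at the first recheck, no other cause | Can be read as discontinue now | Not met before day 14 |
| > 5 × ULN for 2 weeks or more, no other cause | Discontinue | Discontinue |
| > 5 × ULN at first recheck, below 5 × ULN before day 14, no other cause | Can be read as discontinue at the recheck | Not met |
| > 5 × ULN on rechecks, another cause found | Discontinue | Does not apply |

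The two agree only in the second row.

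**Timing, no other cause found.** Inputs: first recheck within 3 days, later ones every 3–4 days, and the 2-week condition (14 days), all from the liver section. Days are counted from the first high value.

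- Judged at a first recheck on day 3, the latest day allowed: 14 − 3 = 11 days. An earlier recheck would lengthen this.
- Judged at the second recheck, on day 3 + 3 = 6 or 3 + 4 = 7: 14 − 6 = 8 or 14 − 7 = 7 days.
- The gap assumes that neither of the other two list scenarios is met. Those carry no duration, and a patient above 5 × ULN is also above 3 × ULN.

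**Another cause found.** No timing gap can be computed, because the list never comes into play. The difference is between discontinuing and having no instruction from the list.

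**Effect on the primary endpoint.** Protocol 8.1 and SAP 3.2 give approximately 50 patients in a 1:1 ratio, so about 50 / 2 = 25 per arm. One patient is 1 / 25 = 4 percentage points of an arm's response rate. In the second row both statements end in discontinuation, so responder status is the same. It can differ only in the third and fourth rows, and then only if drug is later resumed and the patient would otherwise have met the IGF-1 criterion.

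**After the hold.** A value of > 3 and < 5 × ULN leads to a paragraph that permits drug and names no medical-monitor step. Normal or baseline values lead to a required discussion. Two states have no follow-on sentence: a value of exactly 5 × ULN on recheck, and a fall to ≤ 3 × ULN that is neither normal nor back to baseline.

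**The case against.** The strongest reply is that the two statements can be read together. The general sentence leaves the time open, and the 2-week scenario can be taken to supply it. The list is also not worded as exclusive: it gives circumstances in which drug should be stopped and does not say that these are the only ones. On that reading its > 5 × ULN entry is redundant rather than contradictory. This has force on timing. It does not remove the difference on cause, since the general sentence covers patients with another explanation and the list sets them aside. Nor does the text say that one statement defines the other.

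A reader might infer that some patients above 5 × ULN stay on drug under the list. The documents do not support that. Drug is held in all patients at ≥ 5 × ULN, and no sentence lets a patient still above that level take it. The choice is between permanent discontinuation and a continued hold.

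A reader might also infer that a partly recovered patient may restart drug without the medical monitor while a fully recovered one may not. That goes too far. The text never says drug is resumed at > 3 to < 5 × ULN, and permission to continue does not literally fit a patient on hold. One can read it as monitoring on hold, then discussing resumption once values are normal or at baseline. What stands is that the cross-reference does not say whether drug restarts.

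Two further limits stand. The guidance is advisory. And Figure 2, the decision tree, cannot be seen in the copy reviewed; it may settle the order of steps, though the written sentences would still have to agree with it.

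**Conclusion.** The inconsistency is real but narrow. The liver section does not settle when a hold at ≥ 5 × ULN becomes permanent, and its two statements differ on duration and on the role of another cause. The cause difference is the firmer part, because no reading of the duration removes it. The post-hold wording is a secondary ambiguity that rests on a cross-reference.

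With no other cause found, the difference is about 11 days when judged at a day-3 recheck, and may leave the final outcome unchanged. With another cause found, it is discontinuation against no instruction from the list. Each patient whose responder status turns on this moves an arm by about 4 percentage points, assuming 25 per arm. That is a size per affected patient and does not forecast an effect on the trial result: the documents give no expected frequency of ALT or AST at this level, and entry excludes values above 3 × ULN (Protocol 4.2, criterion 15). The OLE consequence is limited too, since a patient whose drug is still withheld for a drug-related event is ineligible under Protocol 4.3, item 2, in any case.

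A clarification is worth making because the matter is hepatic safety and the trial is small. It does not call the design or the primary analysis into question.

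**What to change.** Reconcile the two discontinuation statements in Protocol 7.6 so that they agree on the time above 5 × ULN and on what role another cause plays. Reconcile the two post-hold statements so that it is clear, for each level of recovery, whether resumption is in question and whether the medical monitor is involved. Cover the two states that now have no follow-on sentence. Check the result against Figure 2. Which thresholds, durations and conditions apply is a clinical matter for the sponsor, and none is proposed here.

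The cost is a wording clarification in the protocol. It needs no change to the sample size, the endpoints or the SAP.
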